### 11.1 Patient Registration List

The Patient Registration List is a centre specific document that links each subject to a subject number given by the Investigator. The form is pre-printed with ranked numbers. The Investigator will fill in the subject name, birth date and date for subject enrolment and inclusion into the investigation. The list must not leave the Investigator site. The list will be verified during monitoring or at the final visit.

# Clinical Investigation Plan (CIP)

Study Name: VivaSight-DL study (CIS-009)  
Ethical committee number: S-20180081

CLI-000427

Rev. 02

## 12. SUBJECT DOCUMENTS

### 12.1 Patient Information

The Patient Information (appendix I) is a brief summary of the investigation written in a language understandable for the subject. The Patient Information describes the aim of the investigation, benefits and risks to the subject and the possibility of compensation. Furthermore, it includes an explanation of alternative methods and consequences of withdrawal from the investigation.

The Patient Information reflects current practice in device investigations and is provided according to European regulation, European Medical Directive (2007/47/EC) [1], DS/EN ISO 14155 [2] and Helsinki Declaration [3]. The Patient Information is enclosed in appendix I of this CIP.

The Investigator will review the patient information with each possible subject or legal representative and explain the investigation to him/her during the preparation meeting with the anesthesiologist prior to the surgery. The subject or legal representative will be given sufficient time to consider participation (minimum 30 minutes) and it is recommended that a witness from the patient side is present during the information procedure. Patient Information will be given in the pre-anaesthesia room, where the Investigator, the subject and the subjects relatives can discuss the study in privacy and undisturbed. If the subject requests more time to consider participation in the investigation the Investigator will schedule a new time to obtain Informed Consent. The Patient Information describes the contact details of the investigator.

### 12.2 Informed Consent

Informed Consent (appendix II) is the voluntary confirmation and documentation of the willingness of a subject to participate in a particular investigation, after information has been given orally and in writing to the subject. Point of enrolment is from the time when informed consent is signed. The subject and Investigator must each sign and date the Informed Consent. The subject can be excluded from the study after Informed Consent is obtained in if the subject is assigned a physician with experience in > 50 DLT intubations in patients. This is done, as the subject is not assigned a physician until earliest the day before the surgery. To ensure that the subject has sufficient time to consider participation the Patient Information is given at the preparation meeting which can take place before a physician is assigned.

The Investigator signs to confirm that information has been given to the subject. One copy is for the subject and the other one for the Investigator binder.

A draft version of the Informed Consent is attached to the CIP. A final copy of this Informed Consent must be provided to the Sponsor prior to first use.

Participation in the investigation is voluntary and the subject can at any time chose to be withdrawn from the investigation. This will not have consequences on his/her treatment.

## 13. ADVERSE EVENTS

### 13.1 Definitions

The risks associated to the used of the device have been estimated in an Ambo Product Risk Evaluation following ISO 14971 (7). The residual risks as identified in the risk evaluation, as well as the risks to the subject associated with the procedures of the clinical investigation are balanced against the anticipated direct or indirect benefits for the patient.

#### **Adverse Device Effect (ADE):**

Adverse event relates to the use of an investigational medical device, including events resulting from insufficiencies or inadequacies in the instructions for use, the deployment, the implantation, the installation, the operation, or any malfunction of the investigational medical device. This also includes events resulting from a use error or intentional misuse.

#### **Adverse Event (AE):**

# Clinical Investigation Plan (CIP)

Study Name: VivaSight-DL study (CIS-009)  
Ethical committee number: S-20180081

CLI-000427

Rev. 02

Any untoward medical occurrence, unintended disease or injury or any untoward clinical signs in subjects, users or other persons whether or not related to the investigational medical device.

NOTE 1: This includes events related to the investigational device or the comparator.

NOTE 2: This includes events related to the procedures of the clinical investigation.

NOTE 3: For users or other persons this is restricted to events related to the investigational medical device.

## Device deficiency (DD):

Inadequacy of a medical device related to its identity, quality, durability, reliability, safety or performance, such as malfunction, misuse or use error and inadequate labeling.

## Serious Adverse Device Effect (SADE):

Adverse device effect that has resulted in any of the consequences characteristic of a serious adverse event.

## Serious Adverse Event (SAE):

Adverse event that:

- a) led to a death,
- b) led to a serious deterioration in health that either:
  - 1) resulted in a life-threatening illness or injury, or
  - 2) resulted in a permanent impairment of a body structure or a body function, or
  - 3) required in-patient hospitalization or prolongation of existing hospitalization, or
  - 4) resulted in medical or surgical intervention to prevent life threatening illness or injury or permanent impairment to a body structure or a body function.
- c) led to fetal distress, fetal death or a congenital abnormality or birth defect.

NOTE 1: This includes DD that might have led to a SAE if a) suitable action had not been taken or b) intervention had not been made or c) if circumstances had been less fortunate. These are handled under the SAE reporting system.

NOTE 2: A planned hospitalization for pre-existing condition, or a procedure required by the Clinical Investigation Plan, without a serious deterioration in health, is not considered to be a serious adverse event.

[figure not shown]
## 13.2 Investigator requirements

Investigator must record and document all adverse events in the Adverse Event Form.

### All Adverse Events shall be reported to the Sponsor within three calendar days.

Note that in this case the Investigator is only required to report to the Sponsor, and the Sponsor is responsible of reporting to the Ethics Committee and Competent Authority.

See table below:

Emergency contact details are stated on the form and are as follows:

# Clinical Investigation Plan (CIP)

Study Name: VivaSight-DL study (CIS-009)  
Ethical committee number: S-20180081

CLI-000427

Rev. 02

After termination of the serious adverse event/adverse device effect a copy of all relevant medical documents must be sent to the Sponsor including the finalised Adverse Event Form.

## 13.3 Sponsor requirements

The Sponsor shall report all AE to the Competent Authorities and Ethics Committee with the following timelines (11):

- All serious adverse events (SAE, SADE, USAE, and DD that may lead to a SAE) must be reported to the Sponsor immediately – no later than two calendar days.
- All AE, ADE and DD shall be informed to the sponsor immediately - within seven calendar days after occurrence.

## 13.4 Expected clinical occurrences

The risks associated to the use of the device have been estimated in the Ambu Product Risk Evaluation following ISO 14971 (7). The residual risks as identified in the risk evaluation, as well as the risks to the subject associated with the procedures of the clinical investigation are balanced against the anticipated direct or indirect benefits for the patient.

The clinical benefit from using the VivaSight-DL is continues monitoring of tube position throughout the surgical procedure thus the need of a bronchoscope to confirm tube position can be reduced. Based on these conditions the process can be optimized without compromising patient safety.

## 14. EARLY INTERRUPTION OF THE INVESTIGATION

The Sponsor, Investigator, Regulatory Authority or Ethics Committee may decide to interrupt the investigation in case of detecting repetitive serious adverse events, in case of unexpectedly poor performance of the device, repetitive major deviations from the protocol, etc.

In case of early interruption of the clinical investigation, subjects still in the investigation will be called for a final examination.

## 15. DEVIATIONS FROM THE CLINICAL INVESTIGATION PLAN

The investigator shall record any deviation from the CIP in the CRF together with an explanation for the deviation. Deviations shall be reported to the sponsor who is responsible for analyzing them and assessing their significance.

When relevant, the Sponsor shall inform the ethics committee, competent authorities or the appropriate regulatory bodies of the deviations. Deviations should be reviewed to determine the need to amend the CIP or terminate the investigation.

## 16. RESPONSIBILITIES

The Sponsor is responsible for the investigation as described in the European Standard DS/EN ISO 14155 (6), the MDD Council Directive 93/42/EEC of 14 June 1993 and amendment 2007/47/EC (5).

The monitor of Ambu A/S is responsible for monitoring the investigation as described in section 8 and in compliance with the European Standard DS/EN ISO 14155 (6).

The clinical Investigators are responsible for conducting the investigation as described in the Clinical Investigation Plan, Sponsor-Investigator Agreement (CLI-000424), according to the Helsinki Declaration (8) and ISO 14155 (6).

# Clinical Investigation Plan (CIP)

Study Name: VivaSight-DL study (CIS-009)  
 Ethical committee number: S-20180081

CLI-000427

Rev. 02

## 17. INSURANCE

Ambu A/S will within the limitations of their legal responsibility, accept responsibility for any damage suffered by a subject as a result of using the test products in the clinical investigation as described in this CIP. Ambu A/S is insured in the insurance company IF Skadeforsikring and all subjects will be fully covered throughout the investigation. For further details please see the Investigator Sponsor Agreement (CLI-000424).

## 18. DATA MANAGEMENT AND STATISTICAL ANALYSIS

### 18.1 Sample size

The following formula is used to validate that the chosen sample size is sufficient to detect an effect on the primary outcome):

$$n_1 \geq \left( \frac{(\sigma_{DLT}^2 + \sigma_{vivasight}^2) * (\lambda_z + \lambda_\beta)^2}{(\bar{x}_{DLT} - \bar{x}_{Vivasight})^2} \right)$$

Combined standard deviation and grand mean are based on three studies (2,12,13).

$$\begin{aligned} \bar{x}_{DLT} &= 0,37234 \text{ bronchoscopes used to correct DLT placement} \\ \bar{x}_{vivasight} &= 0,01087 \text{ bronchoscopes used to correct vDLT placement} \\ \sigma_{DLT}^2 &= 0,23622 \text{ bronchoscopes} \\ \sigma_{vivasight}^2 &= 0,01087 \text{ bronchoscopes} \end{aligned}$$

We set power to 90% thus the  $\lambda_\beta = 1.28$  and significance level at 5%  $\rightarrow \frac{0.05}{2} = 0,025 \rightarrow \lambda_z = 1,96$

Thereby, to reject the  $H_0$  the sample size must be:

$$\begin{aligned} n_1 &\geq \left( \frac{(0,23622 + 0,01087) * (1,96 + 1,28)^2}{(0,37234 - 0,01087)^2} \right) = 19,852 \text{ patients} \\ N &= 19,852 * 2 = 39,7035 \rightarrow 40 \text{ patients} \end{aligned}$$

Therefore, a total sample size (N) of 40 generates a power of 90%. A sample size of 50 patients allows a potential dropout rate of 20 percent.

### 18.2 Data management

Case report forms will be completed on paper or electronically and a copy will be stored on site. If data is recorded on a paper format of the CRF, two individuals at Ambu A/S will perform double data entry when the study is terminated. Any unclear data points will be highlighted in a Data Clarification Form that will be sent to the responsible investigator for clarification. An error list will be generated, and errors corrected by Ambu A/S staff. All data will be analysed internally at Ambu A/S.

### 18.3 Statistical analyses

#### 18.3.1 General aspects

Descriptive statistics, i.e. number of subjects, mean, standard error of mean (S.E.M), 95% CI will be presented for continuous data. Categorical data will be summarized using frequency tables (frequency and percent).

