## 18.3.3 Method of statistical analysis in relation to objectives

### Primary outcome:

- Number of times where fiberoptic confirmation of tube position during intubation or surgery is needed

If the observations are normally distributed, a student t-test will be used to examine if number of times the tube position needs to be verified with a bronchoscope is significantly different for procedures using VivaSight-DLT compared to a conventional DLT. If the observations are not normally distributed, a Mann-Whitney U test will be used.

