## 18.7 Health economic evaluation

The cost of all relevant processes related to single-lung ventilation will be summed and the average cost per procedure will create the cost input into a cost-effectiveness model. Capital costs will be discounted at the national appropriate discount rate of 4.05 and depreciated over the assumed life span of the device (14).

The effects measures included in the cost-effectiveness model includes:

- The primary outcome: the risk of needing a bronchoscope to check DLT placement
- The subsequent risk of cross-infection due to bronchoscopy. This risk is calculated based on current evidence from the literature

Cost-effectiveness data will be analyzed as a base-case result via a decision tree running over a short time period of one year within the hospital setting where the procedure is taking place. This will result in the deterministic ICER.

The cost data, risks and base-case will be presented in a table.

To challenge the base-case robustness several 1-way deterministic sensitivity analyses will be conducted. Doing so, major contributors to the base-case result will be varied to test their contribution to the base-case. The one-way sensitivity results will be presented as a tornado plot. To validate the overall robustness and second order uncertainty of the base-case a probabilistic sensitivity analysis will be conducted. Here, all the stochastic variables contributing to the ICER will be varied simultaneously. The probabilistic sensitivity analysis will be presented in a cost-effectiveness plane.

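### For the likeliest test-arm result, no FOB use in 25 patients, an SEM-based 95% CI has zero width; the plan names no interval method that works there

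*Combined protocol and SAP*

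**What the plan says.** Section 18.3.1 (General aspects) states: "Descriptive statistics, i.e. number of subjects, mean, standard error of mean (S.E.M), 95% CI will be presented for continuous data". Categorical data get frequencies and percentages. The section does not say which class FOB use belongs to, and it names no method for the interval.

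Three other places treat FOB use as a numeric quantity:

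- Section 18.1 plans the trial on a mean and a variance per arm. The test-arm mean, 0.01087, is labelled "bronchoscopes used to correct vDLT placement"; the control mean is 0.37234.
- Section 18.3.3 says that, if the data are normal, "a student t-test will be used to examine if number of times the tube position needs to be verified with a bronchoscope" differs between the arms, with Mann-Whitney otherwise.
- Section 18.5 requires the primary outcome to be recorded as an integer.

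Section 18.7 takes the same outcome, now expressed as a risk, into the decision tree. It plans one-way sensitivity analyses and a probabilistic one: "Here, all the stochastic variables contributing to the ICER will be varied simultaneously". It gives no distribution or range for the FOB risk and no rule for a zero count.

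**The concern.** An interval built from the SEM needs some spread in the data. In the test arm the plan expects almost none. The position of VivaSight-DL is checked on the monitor, and FOB is used only if needed (sections 7.5.1 and 7.6), so a count of zero is close to the intended result. A zero count makes the SEM zero and the printed interval a single point. The report would then show the test-arm FOB rate as if it were known exactly, from 25 patients.

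The other route in section 18.3.1, a frequency table, would give the primary outcome no interval at all. Neither route yields usable error bars for the likeliest test-arm result. FOB incidence carries the study hypothesis (section 3) and is an effect input to the cost-effectiveness model, so its uncertainty should be stated properly.

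**Working it through.** **Inputs.** From section 18.1: means 0.37234 (control) and 0.01087 (test); variances 0.23622 and 0.01087; multipliers 1.96 and 1.28; 20% dropout. From section 5.2: 25 patients per arm.

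**The plan's own figure.** n per arm = (0.23622 + 0.01087) × (1.96 + 1.28)² / (0.37234 − 0.01087)² = 0.24709 × 10.4976 / 0.13066 = 19.852, so N = 39.70, rounded to 40, and 40 / 0.8 = 50. This reproduces.

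**What the inputs are.** 35/94 = 0.37234 and 1/92 = 0.01087. The sample variance of a 0/1 variable with those counts is 35 × 59 / (94 × 93) = 0.23622 for control and 1/92 = 0.01087 for test. The planning figures therefore behave as proportions, with one event in 92 for the test arm.

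**Chance of a zero count.** Expected uses in the test arm = 25 × 0.01087 = 0.27. P(0 of 25) = (1 − 0.01087)^25 = 0.761. P(1 of 25) = 25 × 0.01087 × (1 − 0.01087)^24 = 0.209. P(0 or 1) = 0.970. With 20 patients, P(0) = 0.804.

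**The SEM-based interval** (mean ± t × SEM, t = 2.064 on 24 df):

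| Uses in 25 | Mean | SEM | SEM-based 95% CI | Clopper-Pearson 95% CI |
|---|---|---|---|---|
| 0 | 0 | 0 | 0 to 0 | 0 to 13.7% |
| 1 | 0.04 | 0.04 | −0.043 to 0.123 | 0.1% to 20.4% |

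The exact upper limit for 0/25 is 1 − 0.025^(1/25) = 0.137. For mean uses, the exact Poisson upper limit is −ln(0.025)/25 = 0.148 per patient. The interval for one use extends below zero, which is impossible for a count.

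**Coverage.** I summed the binomial probabilities of those counts (0 to 25) whose SEM-based interval contains the true rate. The interval misses whenever the count is zero and contains the true rate at one use.

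| True rate | P(0 of 25) | Coverage (nominal 95%) |
|---|---|---|
| 1/92 | 76% | 24% |
| 2% | 60% | 40% |
| 5% | 28% | 72% |

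P(0 of 25) falls to 50% at a rate of 1 − 0.5^(1/25) = 2.7%.

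**Effect on the comparison.** Take 0/25 against 9/25, close to the planning rates. The control variance is 0.36 × 0.64 × 25/24 = 0.24, so its SEM is √(0.24/25) = 0.098. The Welch interval for the difference is 0.36 ± 2.064 × 0.098 = 0.158 to 0.562. Newcombe's interval, which is valid at zero, is 0.154 to 0.555; the score interval is 0.201 to 0.557. The test arm carries only 0.01087 / 0.24709 = 4.4% of the planning variance, so its zero SEM matters little here.

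**Effect on the sampled risk difference.** Beta(9.5, 16.5) for control has variance 9.5 × 16.5 / (26² × 27) = 0.00859. Beta(0.5, 25.5) for test has variance 0.5 × 25.5 / (26² × 27) = 0.00070. Adding the second raises the SD by √(0.00929 / 0.00859) = 1.04, about 4%.

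**The case against.** **The premise is an inference.** Section 18.3.1 speaks of continuous data, FOB use is an integer count, and no interval method is named. That is fair. But the planning means and variances and the t-test point to the mean/SEM route, and the only alternative offered has no interval.

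**The planning rate may not be the trial rate.** It is for scopes used to correct placement, whereas the endpoint is FOB confirmation needed during intubation or surgery, here by novices. This stands: above about 2.7%, zero is no longer more likely than not. It weakens the 76%, but coverage is still well short of 95% at 2% and at 5%.

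**The main comparison is hardly touched.** A reader might infer that the primary analysis fails. It does not: Mann-Whitney remains usable, and the control arm supplies nearly all the variance of the difference. That reassurance holds at the planning rates only. Sections 7.5.2 and 7.6 build FOB checks into the control procedure, so on the scale of at least one use the control arm could approach 25/25, where its SEM would collapse too.

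**The economic model.** A reader might infer that it will treat the test-arm risk as known. Section 18.7 does not say so. It plans to vary all stochastic inputs, and never states that the sample SEM, or a Beta(0, 25), would be the input. Beta(0, 25) is not even a proper distribution. Fixing the risk at zero is a possible result of leaving the distribution open, not a planned one. No material understatement of the uncertainty of the ICER has been shown.

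**Conclusion.** The concern holds for the test-arm interval. With 25 patients and the plan's own rate, zero uses is the likeliest outcome (about 76%). An SEM-based interval is then 0 to 0, where exact methods allow up to 13.7%, or 0.148 uses per patient. Its coverage is about 24% at the planning rate.

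This rests on three assumptions: that FOB use gets the mean/SEM summary, that the interval is the usual t-based one, and that the true rate is near 0.01087. The coverage figures also take at most one use per patient, as the planning variances imply.

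For section 18.7 the conclusion is narrower: a distribution and a zero-count rule are missing, and should be chosen before the data are seen, since section 18.2 has the sponsor analyse the data internally. The point should be fixed, but it does not undermine the primary test or, at the planning rates, the between-arm estimate.

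**What to change.** **Section 18.3.1.** Add a rule for FOB use:

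- For each arm, report the proportion of patients with at least one use, with a Clopper-Pearson 95% CI.
- For each arm, report mean uses per procedure with an interval that remains valid at a zero count. Exact Poisson suits the test arm. It need not suit the control arm, where checks are built into the procedure.
- Report the between-arm risk difference with a score or Newcombe 95% CI, naming which one.

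**Section 18.7.** Name the distribution from which the FOB risk is sampled, and choose one that stays proper at 0/25. Beta(r + 0.5, n − r + 0.5), with r the patients with at least one use and n the arm size, is one choice; at 0/25 its 97.5% limit is 9.5%. Beta(1, 26) would give 13.2%. The choice is partly convention, which is a reason to settle it in advance.

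**Cost.** A few sentences of wording and no new data: the CRF already records the number of bronchoscope uses in each phase. The downside is a wider test-arm interval.

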#### 18.3.2 Handling of dropouts and missing data

Data from intermediate dropouts, who has been intubated but not undergone surgery will not be included within the analysis of the primary outcome. Furthermore, data from intermediate dropouts will be included until dropout. Early dropouts, who dropout prior to intubation will be excluded from all analysis.

Potential missing data points will be explored and substituted via regression imputation or listwise deletion as appropriate. Using substitutions via regression imputation the existing variables are used to make predictions for the missing values. As a result, the data is retained, and significant altering of the standard deviation is avoided. To examine whether potential missing data points are missing at random, or whether they could lead to a potential bias, an independent sample t-test will be applied, comparing the remaining variables of the observations with full data and the observations with missing data.

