## 6.4 Recruitment

The subjects included in this investigation will be under treatment in department V at OÜH, and clinically judged by the investigator to be eligible for a single-lung ventilation. The subject, or if the subject is unable to, the subject's legal representative, will receive information orally and in writing about the investigation (see Patient Information, appendix I) from an Investigator (nurse or physician with at least two years of experience in anesthesia). Patient Information will be given in the pre-anaesthesia room, where the Investigator, the subject and the subjects relatives can discuss the study in privacy and undisturbed. If the subject agrees to participate they must sign the Informed Consent (see Informed Consent, appendix II) before start of the investigation.

A subject is considered included in the investigation as soon as informed consent has been signed. If subject or their legal representative do not consent to the investigation the procedure will be performed regardless, however off this investigation.

When a subject is included the Investigator assures that the subject meets all inclusion criteria and none of the exclusion criteria, by checking the relevant boxes in the CRF.

Participation in the investigation is voluntary and the subject or the subject's legal representative can at any time withdraw from the investigation without any consequence for further examinations and treatment.

If a subject withdraws from the investigation the subject will be replaced to ensure that the total number of subjects included in the analysis reach 50 subjects. If any data was recorded before withdrawal, this will be stored in the investigator binder but not used for analysis. When a subject is replaced the new subject is given a new subject number.

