## 11. CLINICAL INVESTIGATION PLAN

The CIP was made according to the Council Directive 93/42 EEC of 14 June 1993 and amendment 2007/47/EC (5), the guidelines set out in ISO 14155 (6), ISO 14971 (7), and the Helsinki Declaration (8).

An example of the Case Report Form is enclosed in the CIP together with the Patient Information and Informed Consent. The Case Report Form is in English and should be filled in English when possible. Missing data not recorded on the day of the procedure should be filled in later accompanied by date and signature. Data that are evaluated as incorrect by Investigator should be crossed over with ink allowing the "old data" to be seen (example). The Investigator shall then write the new and correct data and then sign and date.

Any discrepancies compared to the procedures described in this CIP shall be documented and reported to the Sponsor or monitoring person.

The Sponsor and the Investigator must sign the CIP before the investigation can start at the centre.

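### Section 18.3.2 fills missing values with regression predictions on an SD claim that holds only when very few values are missing, and its t-test check cannot show data are missing at random (minor)

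*Combined protocol and SAP*

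**What the plan says.** CIP section 18.3.2 says missing points will be "substituted via regression imputation or listwise deletion as appropriate". It describes the method as follows: "Using substitutions via regression imputation the existing variables are used to make predictions for the missing values". It then draws the conclusion at issue: "As a result, the data is retained, and significant altering of the standard deviation is avoided". It does not list predictors, does not say whether arm is one of them, mentions no residual draw or multiple imputation, and gives no rule for choosing between imputation and deletion. No missing rate, R² or reference supports the SD statement.

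The same section plans an independent-samples t-test of the other variables, comparing complete with incomplete observations. Its purpose opens with "To examine whether potential missing data points are missing at random" and extends to whether the gaps could cause bias.

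The results feed section 18.3.1, where "mean, standard error of mean (S.E.M), 95% CI will be presented for continuous data", and the t-test or Mann-Whitney comparisons of section 18.3.3. Section 18.5 requires the primary outcome in integers.

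**The concern.** A regression prediction lies on the fitted line. Filling gaps with predictions leaves out the residual scatter that real values would have had, so the stated reason for using the method is the opposite of its usual weakness. The filled values are then counted as if observed, so the sample size is overstated as well as the spread understated.

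Whether arm is in the model changes the kind of error. With arm in, standard errors are too small and the test is too liberal. With arm omitted, each filled value is pulled towards the pooled mean and the difference between arms is diluted. That dilution would also carry into the cost-effectiveness model of section 18.7, which uses the primary outcome. Because the choice is left open, it could be made after the data are seen.

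The t-test check raises a separate problem: a non-significant result could be taken as reassurance that it cannot give.

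**Working it through.** **The plan's own figure.** Section 18.1 reproduces: (0.23622 + 0.01087) × (1.96 + 1.28)² / (0.37234 − 0.01087)² = 19.852 per arm, or 40 in total, and 40 / (1 − 0.20) = 50. The sample size does not depend on the present point. The planning figures match 35 of 94 and 1 of 92 subjects (35/94 = 0.37234; 1/92 = 0.01087; the sample variances also agree), so a 0/1 outcome is used below as one test case.

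**Inputs.** From the CIP: 25 per arm (5.2), two-sided 5% (18.3.4), t-test or Mann-Whitney (18.3.3). Assumed, because the documents do not give them: values missing completely at random; missing share m of 4%, 10% or 20% (2, 5 or 10 of 50); R² of 0.1 for the continuous case. The 20% in section 18.1 is a dropout allowance, not an item-missing rate.

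**SD and SEM, arm in the model or no true difference.** Observed values have variance σ² and filled values about R²σ², so

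- SD ratio = √(1 − m(1 − R²)): √0.964 = 0.98, √0.91 = 0.95, √0.82 = 0.91.
- SEM relative to the complete-case SEM = SD ratio × √(1 − m), because 25 is used instead of 25(1 − m): 0.982 × 0.980 = 0.96; 0.954 × 0.949 = 0.91; 0.906 × 0.894 = 0.81.

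Simulation gives SD ratios of 0.98, 0.95 and 0.90, SEM ratios of 0.96, 0.90 and 0.81, and 95% CI coverage of 94%, 93% and 89%.

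**Tests (simulated, 25 per arm).**

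| | 4% | 10% | 20% |
|---|---|---|---|
| Arm in, t-test, normal data: type I error | 5.8% | 7% | 11% |
| Arm in, Mann-Whitney, 0/1 data at 0.372 in both arms, unrounded | 5.4% | 6.4% | 8.3% |
| Same, predictions rounded to integers | 7% | 10% | 17-18% |
| Arm omitted, t-test: type I error | about 5% | about 5% | about 5% |
| Arm omitted: true 1-SD difference estimated as | 0.96 | 0.90 | 0.80 |

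Complete cases gave 4-5% type I error and an unbiased estimate. The simulation error is about 0.3 percentage points at a 5% rate. Repeat runs agreed to within about one point, except that the 20% rounded figure ranged from 15% to 18%.

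With arm omitted, the planned difference of 0.36147 would be estimated as about 0.36147 × (1 − m) = 0.35, 0.33 and 0.29. The SD then need not shrink: at the section 18.1 values the VivaSight SD rises by 5-7% at 4% missing, because values near the pooled mean are placed in an arm with almost no spread.

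**The t-test check.** It compares observed variables only. In simulation (50 subjects, R² 0.1, an assumed strong selection), it flagged 5% of trials when data were missing completely at random. When missingness depended on an observed covariate, it flagged 47%, 85% and 97% at 4%, 10% and 20% missing, with complete-case bias of 0.02, 0.04 and 0.08 SD. When missingness depended on the unseen outcome, it flagged only 9%, 14% and 19%, with bias of 0.05, 0.12 and 0.24 SD. It therefore reacts most where the harm is least. A significant result is compatible with missing at random, and a non-significant one does not rule out bias.

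**The case against.** The sentence claims only that significant altering is avoided, and at 4% missing it is close to true. The plan gives good reason to expect few gaps. Bronchoscope counts are entered on the CRF during the procedure. On late entries, section 11 says: "Missing data not recorded on the day of the procedure should be filled in later accompanied by date and signature". Unclear data are queried (18.2). Withdrawn subjects are replaced, and section 6.4 adds: "If any data was recorded before withdrawal, this will be stored in the investigator binder but not used for analysis". Intermediate dropouts leave the primary analysis (18.3.2). All of this stands, and it is why the point is minor.

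It is also fair that a stochastic imputation is not excluded in words, and that existing variables could include arm. But the text describes predictions and nothing more, and with arm included type I error is inflated.

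The t-test is planned as an examination, with no decision rule attached. That limits the harm but does not make it a test of missing at random.

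A reader might infer two stronger things. One is that the primary test would run at 11%, or at 17-18% with rounding. Those figures need 20% item-level missingness, which no document suggests. The other is a loss of power. With arm omitted and non-integer filled counts, simulated Mann-Whitney power on 0/1 data was 92%, 83% and 71%, against 97%, 95% and 92% for complete cases. This does not hold up. Section 18.5 requires integers, and rounding restored power to about 97%, 96% and 92%. A 0/1 control outcome also sits badly with the routine bronchoscope checks for controls in sections 7.5.2 and 7.6. If those checks count, each control has at least two uses, and simulated power was 100% at all three rates. No power loss should be claimed.

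**Conclusion.** The point holds as a minor one. As described, the imputation does not generally preserve the SD. The claim is roughly right at about 4% missing when arm is in the model, and it fails as missingness grows. The error is either too liberal a test (arm in) or a difference diluted by about the missing share (arm omitted), and the plan does not say which model applies. At the low missing rate that the plan's safeguards suggest, the effect is about 2% on the SD and under one percentage point on t-test type I error, or about two points for Mann-Whitney if predictions are rounded to integers.

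These sizes rest on assumed missing rates, an assumed R² of 0.1 for the continuous case, and data missing completely at random. The conclusion about the t-test check needs none of these: no comparison of observed variables can establish missing at random.

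**What to change.** In section 18.3.2:

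- Delete prediction-only regression imputation and the sentence about the SD.
- State one rule: each outcome is analysed in subjects with that outcome recorded, and the number missing is reported by arm. The section already allows this as listwise deletion, and it avoids non-integer filled counts.
- If imputation is kept, use multiple imputation with arm in the model, as a sensitivity analysis only. In simulation this held type I error at 4.4-5.0% and matched complete cases on power, so it adds little as a primary method.
- Describe the t-test as a descriptive comparison of complete and incomplete cases, not as a test of missing at random or of bias.

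A best/worst-case analysis by arm, should any bronchoscope count be missing, is optional.

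The cost is SAP wording and little analysis work. Intervals become slightly wider than the imputed ones (about 1/0.96, or 4%, at 4% missing). Complete-case means can carry a small bias if missingness depends on an observed covariate: 0.02 to 0.08 SD in the strong-selection scenario above.
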